6.4.3 Vaccine efficacy (VE) analyses against SARS-CoV-2 infection

The time origin for all analyses of SARS-CoV-2 infection is enrollment. We define the time of diagnosis of the SARS-CoV-2 infection endpoint as the collection time of the first daily swab with a positive PCR test. The time of diagnosis of lab-confirmed clinical COVID-19 disease is the first time of reported qualifying COVID-19 symptoms that occurs simultaneously or after the diagnosis of the SARS-CoV-2 infection endpoint. The time of diagnosis of asymptomatic SARS-CoV-2 infection is the collection time of the first sample with a positive PCR test result or seroconversion without any prior or subsequent reporting of symptoms that led to confirmation of a COVID-19 disease endpoint. The time of diagnosis of SARS-CoV-2 seroconversion is the collection time of the first sample seropositive for SARS-CoV-2, for participants SARS-CoV-2 seronegative at baseline; the SAP will specify criteria for defining seroconversion (re-infection)

for individuals SARS-CoV-2 seropositive at baseline. The failure times of participants never observed to be diagnosed with a given clinical endpoint will be right-censored at the date of last contact at which endpoint status was assessed or study termination. The failure times of participants reporting receipt of COVID-19 vaccination outside the study will be right-censored at the date of first outside vaccination.

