Appendix E Procedures for Main Cohort, Immediate Vaccination Group

Visit:	01 ¹	02 ²	03	04	05	06
Day:		D1	D29	D57	D113	D141
Week:		W0	W4	W8	W16	W20
Month:		M0	M1	M2	M4	M5
Procedure	Scr.	VAC1	VAC2			
Study procedures						
Screening consent (if used)	✓	—	—	—	—	—
Assessment of understanding	✓	—	—	—	—	—
Protocol consent (eConsent)	✓	—	—	—	—	—
Medical history questionnaire ³	✓	✓	—	—	—	—
SARS-CoV-2 infection risk assessment ³	✓		Weekly			
COVID-19 symptom surveillance ³	—		Weekly starts at week 2, not during week 5			
Confirm eligibility	✓	—	—	—	—	—
Obtain demographics ³	✓	—	—	—	—	—
Randomize	—	✓	—	—	—	—
SARS-CoV-2 testing questionnaire ³	—		approximately 2x per week			
End of study questionnaire ³	—	—	—	—	✓	—
Research Samples⁴						
Serum for Immunogenicity Assays and Storage	—	✓	—	✓	—	—
Serum for SARS-CoV-2 clinical serology ⁵	—	✓ ⁶	—	✓ ⁶	✓	—
Nasal swab	—		Daily ⁷			
Vaccination procedures						
COVID-19 symptom check ⁸	—	✓	✓	—	—	—
Vaccination	—	✓	✓	—	—	—

Greyed out visit column does not apply to this group.

1 Screening may occur over the course of several contacts/visits up to and including day 1, prior to vaccination.

2 Blood draws required at vaccination visits must be performed prior to vaccination.

3 Results from screening at school, if applicable, or at other locations will be captured via eDiary, please see Section 9.16.

4 From screening to the final study visit, the total blood volume to be collected from each participant will be approximately 40 mL (maximum) with a maximum of approximately 17 mL collected in a single visit.

5 For blood self-collected by a participant the maximum volume will be less than 1 mL in a single collection.

6 SARS-CoV-2 clinical serology testing may be performed on leftover blood from samples collected for immunogenicity assays. No separate blood sample is needed. If a Main cohort participant is also in the Prospective Close Contact (PCC) cohort related to

an index case or in the Case-ascertained Close Contact (CACC) cohort, one additional blood collection (self-collection) will be performed (see table below).

7 Daily swabs will be collected from vaccination through D113. Swabs will be returned via drop-off location(s) specified by the clinic or through the mail.

8 COVID-19 Symptom Check to be performed within 24 hours prior to vaccination.

The following **additional** procedures will occur for Main cohort, immediate vaccination participants, who fall under any of the following categories:

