7.1 Descriptive analysis

Tables

The following table will be used to describe SARS-CoV-2 incidence by group and vaccine receipt. It will be produced first including only baseline SARS-CoV-2 negative participants, and then again including all FAS-P participants. Each participant's incident exposure period will start from either the first nasal swab (if the first swab result was negative) or 90 days after the first swab (if first swab positive). The participant's exposure will be broken down to unvaccinated, one-dose and two-dose exposure periods. The unvaccinated exposure period will include days and events up to (and including) the date of the first study vaccination or censoring, whichever occurs first. The one-dose exposure period will include days and events starting the day after the first vaccine and ending on the date of the second vaccine or censoring, whichever occurs first. The two-dose exposure period will include days starting the day after the second vaccine. The 95% confidence interval for the incidence rate will be calculated using the exact method.

Group	Exposure: number of study vaccine doses	Censoring	Number of incident infections	Person- years	Incidence rate (95% CI)
Immediate arm	Unvaccinated	Outside vaccination		See note 1	
	Unvaccinated	ITT		See note 1	
	Single dose	Outside vaccination		See note 2	
	Single dose	ITT		See note 2	
	Two doses	Outside vaccination		See note 3	
	Two doses	ITT		See note 3	
SoC arm	Unvaccinated	Outside vaccination		See note 4	
	Unvaccinated	ITT		See note 4	
Vaccine Declined arm	Unvaccinated	Outside vaccination		See note 4	
	Unvaccinated	ITT		See note 4	

Note 1: Total number of person-years from the incident follow-up start to the first of study vaccination, infection or censoring.

Note 2: Total number of person-years from the last of incident follow-up start and first dose to the first of second dose, infection or censoring.

Note 3: Total number of person-years from the last of incident follow-up start and second dose to the first of infection or censoring.

Note 4: Total number of person-years from the incident follow-up start to the first of infection or censoring.

Incident follow-up start = either the first nasal swab (if the first swab result was negative) or 90 days after the first swab (if first swab positive)

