7.2 Primary efficacy analysis

Objective: To evaluate the effect of mRNA-1273 vaccination on acquisition of SARS-CoV-2 infection

Endpoint: Incident infection by study PCR subject to Outside Vaccination Censoring.

Data sets: Baseline SARS-CoV-2 negative participants enrolled as randomized

Exposure: Randomization, and number of study vaccine doses received within the Immediate Vaccination group

Adjustment covariates: Baseline factors: Age, sex, race/ethnicity, place of residence, attributes from the Baseline SARS-CoV-2 Infection Risk Assessment CRF

Analysis: Vaccine efficacy will be estimated using a time-varying Cox model that stipulates the following hazard function

$$h(t) = h_{0S}(t) \exp \{ \alpha_1 I(T_1 < t) + \alpha_2 I(T_2 < t) + \beta X \}$$

where t is time since study initiation (calendar time), T_1 is the calendar time of the first dose of study vaccine and T_2 is the calendar time of the second dose of study vaccine, $h_{0S}(t)$ is an unspecified baseline hazard that depends on study site, and X is a vector of baseline covariates identified in Section 3.2.5 and 3.2.6 as associated with exposure and/or censoring. The efficacy of one dose of study vaccine will be measured by $1 - e^{\alpha_1}$ and the efficacy of two doses measured by $1 - e^{\alpha_2}$. The model will be fit using the R survival package. Two-sided 95% confidence intervals for the VE estimates will be calculated using the Wald method.

If the set of covariates that is associated with SARS-CoV-2 exposure and/or censoring is too large to permit covariate adjustment, an IPCW analysis will be performed. Specifically, the above Cox model will be fit using a time-dependent weight that corresponds to a (standardized) probability of censoring. The analysis will be implemented using the R ipcswitch package.

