9.2 To evaluate the efficacy of Moderna COVID-19 Vaccine to against COVID-19 disease

Objective: To evaluate vaccine efficacy against COVID-19 disease, (i.e., to evaluate VED).

Outcome: PCR-confirmed COVID-19 diagnosis where symptomology on a given day as reported by e-diary (weekly or daily) occurs no more than 3 days prior to and no more than 14 days after the administration of the first nasal swab that is PCR positive. This represents a slight departure from the protocol that only relies on weekly testing to expand to also include daily symptom questionnaires that start after a positive test to increase precision of the disease definition.

Data sets:

Definition of Endpoint: COVID-19 is defined as symptomatic disease based on the following criteria as assessed in daily and weekly self-reported symptom logs, coincident with virologic confirmation (RNA PCR Ct < 40):

- at least one of the following signs/symptoms: hospitalization, fever, chills, cough, shortness of breath, difficulty breathing, tiredness/fatigue, muscle aches, joint aches, body aches, headache, change in sense of taste, change in sense of smell, sore throat, nasal congestion, runny nose, nausea, vomiting, diarrhea, oral ulcers (mouth sores) and clinical or radiographical evidence of pneumonia

This definition defers from the primary endpoint definitions in the phase 3 COVID vaccine trials (e.g. COV-19 3001) and the protocol because some symptoms were not collected (thromboembolic event, myocardial infarction, myocarditis, chilblains, or multi-inflammatory syndrome) and symptom diaries for some participants were incomplete and/or not collected during the specified time interval.

Symptom onset date will be defined as the first symptomatic day according to the daily or the weekly symptom log that is in the interval starting no more than 3 days prior to and no more than 14 days after the first positive nasal swab. We will assume symptomatic logs represent symptom presence on the day of the log for the daily logs and in the period between a given log and the preceding log (or enrollment if no preceding log) for weekly logs. The latter assumption may be violated if participants experienced the symptom only for part of the period (cannot be determined from the log).

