A participant will be defined as having reached the endpoint if they have the diagnosis above. The time of the endpoint will be the onset of symptoms. Participants who do not have the endpoint will be censored at the earlier of first positive PCR without symptoms (or with missing symptom logs) and outside vaccination censoring. As a supportive analysis, we will also consider censoring at the earlier of first positive PCR without symptoms and ITT censoring. Death and hospitalization with positive PCR will be counted in the endpoint.

Analysis Details:

A participant will be defined as having reached the endpoint if they have the diagnosis above. The time of the endpoint will be the onset of symptoms. Participants who do not have the endpoint will be censored at the last time they were known to be symptom- and infection-free. Death and hospitalization will be counted in the endpoint. Rate tables and VE estimation analogous to analyses of the acquisition endpoint will be produced. The same set of covariates will be adjusted for in VE estimation as for the acquisition endpoint.

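### Dating COVID-19 disease at symptom onset can place a PCR-dated infection in the wrong dose period, or at or before the start of follow-up; the net direction of bias is not established

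*SAP*

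**What the plan says.** SAP 9.2 counts a PCR-confirmed infection as disease if its symptoms fall in a window around the first positive swab, "no more than 3 days prior to and no more than 14 days after the administration of the first nasal swab", and it fixes the event date by this rule: "The time of the endpoint will be the onset of symptoms". Onset is the first symptomatic day in either the daily or the weekly log. A symptomatic weekly log is taken to mean symptoms "in the period between a given log and the preceding log (or enrollment if no preceding log) for weekly logs", within the same window.

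The analysis is borrowed from the infection endpoint: "Rate tables and VE estimation analogous to analyses of the acquisition endpoint will be produced". The tables in SAP 7.1 split time by dose: "The one-dose exposure period will include days and events starting the day after the first vaccine and ending on the date of the second vaccine". Censoring closes that period if it comes sooner. Two-dose time runs from the day after dose 2. Follow-up starts at the first swab if that swab is negative. The Cox model in SAP 7.2 switches at T1 and T2, where T1 "is the calendar time of the first dose of study vaccine" and T2 is the same for dose 2. Infection itself is dated at collection of the first positive study swab (SAP 7).

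Protocol 6.4.3 dates disease at the first qualifying "symptoms that occurs simultaneously or after the diagnosis of the SARS-CoV-2 infection endpoint".

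**The concern.** The two endpoints use different clocks, and dose status is read from each endpoint's own clock. An infection that study PCR places before a dose can appear as disease after that dose, although the dose could not have prevented it. The reverse can also happen. SAP 9.2 has no rule that carries dose status over from the swab, and none for an onset that precedes follow-up.

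At stake are dose-specific VE_D and its agreement with VE_S on which dose period an infection belongs to. Onset dating is not wrong in itself. The difficulty comes from combining it with exposure that changes at each dose and with a start of follow-up defined by swabs.

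**Working it through.** The documents give no event count, power or VE figure for the disease endpoint, so there is nothing of the plan's own to reproduce.

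**1. What the rule allows, day by day.** Let p be the day of first positive and L the onset lag, from -3 to +14.
- Forward crossing: p on or before the dose day, p + L after it. This is possible for positives from 13 days before the dose up to the dose day, 105 combinations of p and L. Example: positive Day 28, dose 2 on Day 29, first symptoms Day 31 known only from the daily diary. This is infection in one-dose time and disease in two-dose time.
- Backward crossing: p 1 to 3 days after a dose, p + L on or before it. 6 combinations.
- Entry: with the first negative swab as day 0, onset falls before day 0 for (p, L) = (1, -2), (1, -3), (2, -3), and exactly on day 0 for (1, -1), (2, -2), (3, -3). Neither group has time at risk in the Cox fit.

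**2. Effect on two-dose VE_D.** Assumptions not in the documents: constant background hazard (set to 1), true VE 50% after one dose and 90% after two, and the onset lags below. Days 1, 29 and 113 in Protocol Appendix E give 28 one-dose and 84 two-dose days. VE here is a rate ratio against unvaccinated time.

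Two-dose events = 0.10 × 84 + 0.50 × F − 0.10 × B, where F is the mean forward lag and B the mean backward lag. VE = 1 − events/84.

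*Exact onset dates, every dose given before the result is known, fixed lag d (F = d, B = 0):*
- d = 1: 8.9/84, VE 89.4%
- d = 3: 9.9/84, VE 88.2%
- d = 5: 10.9/84, VE 87.0%

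*Weekly logs all filed, evenly spread, so that onset is back-dated 0 to 6 days and floored at −3:*
- d = 1: recorded lags 1, 0, −1, −2, −3, −3, −3; F = 1/7, B = 12/7; events 8.400 + 0.071 − 0.171 = 8.300, VE 90.1%
- d = 3: lags 3 down to −3; F = B = 6/7; events 8.743, VE 89.6%
- d = 5: lags 5 down to −1; F = 15/7, B = 1/7; events 9.457, VE 88.7%

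If the day of the preceding log also counts (back-dating 1 to 7 days), these become 90.3%, 89.9% and 89.2%. At d = 1 the sign reverses.

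*Lag spread uniformly, no weekly back-dating, dose 1 on the first-swab day:*
- −3 to +3: VE 89.6%; 5% of two-dose disease events were PCR-positive by dose 2
- −3 to +7: 88.5%; 13%
- −3 to +14: 86.6%; 26%

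With true two-dose VE of 50%, the same three cases read 50.0%, 48.8% and 46.7%.

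**3. One-dose VE_D.** At d = 3 with exact dates, one-dose events are 0.5 × 28 − 0.5 × 3 + k × 3. Here k = 0 if nobody is followed before dose 1 and k = 1 if everyone is. VE is 1 − 12.5/28 = 55.4% or 1 − 15.5/28 = 44.6%, so it can move either way.

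**4. Events dated at or before entry.** Under the uniform lags above, and with 0 or 7 days of follow-up before dose 1, 0 to 1.5% of Immediate-group events fall before entry and a similar share on the entry day. With back-dating of 0 to 6 days and dose 1 at entry, the share is 0.5 × B/(14 + 8.4): 3.8%, 1.9% and 0.3% for d = 1, 3, 5. Back-dating of 1 to 7 days raises the first to 4.8%. In unvaccinated time the d = 1 figure is (12/7)/112 = 1.5%. In the limiting case every positive in the first 3 days is affected. Over two equal arms that is (3 + 1.5)/(112 + 22.4) = 3.3%; the Immediate group alone would have 1.5/22.4 = 6.7%, because its hazard is concentrated early.

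**The case against.** A reader might infer that two-dose VE_D is biased downward, by as much as the 30% inflation in two-dose cases implied by a 5-day delay (0.5 × 5/8.4). The documents do not support that, for four reasons.

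- The weekly-log rule dates onset earlier, which reduces forward crossing and creates backward crossing.
- In the Immediate group, weekly symptom surveillance pauses after dose 2 (Protocol 9.15; week 5 in Appendix E). Take a Day 27 positive with symptoms on Day 30. A symptomatic log filed after the pause normally reaches back before the dose, so recorded onset falls on Days 24 to 29, which is one-dose time. Forward crossing then needs onset known from the daily diary alone, or a preceding log dated on or after the dose. SAP 9.2 itself says some diaries were incomplete, so this can occur but is not the rule.
- Giving every dose before the result is known is a worst case. The protocol describes real-time testing, and Protocol 9.7 applies CDC vaccination guidance once infection is diagnosed. These safeguards are partial. Swabs return by drop-off or mail, and the pre-dose step in Appendix E, "COVID-19 Symptom Check to be performed within 24 hours prior to vaccination", does not detect a pre-symptomatic infection.
- Protocol 6.4.3 also dates disease at symptoms and allows onset after the first positive. It conflicts with the SAP only on the 3-day look-back and gives no support against forward crossing.

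It would also go too far to say that VE_S and VE_D cannot be compared; some infections change dose period between them. Finally, the endpoint is secondary, the randomized analyses are declared post hoc (SAP 2.4) and the study is underpowered (SAP 2.5), so shifts of this size are small beside sampling error. All of this limits size and direction. None of it supplies the missing rule.

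**Conclusion.** The point holds as a defect in the event-time rule. Followed as written, SAP 9.2 can move a PCR-dated infection across a dose in either direction, or date it at or before entry so that the Cox fit loses it. The net direction of bias in VE_D is not established: forward crossing lowers two-dose VE_D, while back-dating and backward crossing offset it.

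With assumed true VE of 50% and 90%, the shift in two-dose VE_D is about 0 to 3 points. The upper end needs exact onset dates and every dose given before the result is known. Events dated at or before entry are roughly 0 to 4%, depending on log timing. These figures rest on assumed lags and efficacies; the documents do not say how many events are affected. The primary infection endpoint is not touched.

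**What to change.** In SAP 9.2, use the symptom window only to classify an incident infection (SAP 3.2.2) as symptomatic. Set event time and dose status to the collection date of its first positive study swab, and report the onset date descriptively. Each infection then falls in the same dose period for VE_S and VE_D. None precedes follow-up, because an incident positive must follow a negative swab.

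If onset dating is kept, use the later of onset and first positive swab, and carry dose status from the first positive swab.

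In the same edit, reconcile the two censoring rules that SAP 9.2 gives for participants without the endpoint: first positive PCR without symptoms or outside-vaccination censoring, against the last time known free of symptoms and infection.

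The cost is SAP wording and one derived variable, with no new data. The small downside is that the event time is no longer the onset date.

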9.15 COVID-19 symptom surveillance for Main Cohort

Participants will be monitored for symptoms of COVID-19 throughout the course of the study via a weekly eDiary. These symptoms will be used to establish whether a participant meets criteria for COVID-19 disease as defined by Secondary Endpoint 4. If a participant has symptoms consistent with COVID-19, they will be encouraged to seek testing and clinical care through their local testing and care facilities. Results of testing will be reported through the eDiary and participants who have positive test results will follow procedures described in Section 9.7.

For Immediate Vaccination Group only: due to the overlap of symptoms that can result from vaccination and symptoms of COVID-19, monitoring will begin 7 days following the first study product administration. Symptom monitoring will be paused 7 days following the second product administration.

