Appendix F Procedures for Main Cohort, Standard of Care and Vaccine Declined Groups

Visit: Day: Week: Month: Procedure	01 ¹ Scr.	02 D1 W0 M0	03 D29 W4 M1	04 D57 W8 M2	05 D113 W16 M4 VAC1	06 D141 W20 M5 VAC2
Study procedures						
Screening consent (if used)	✓	–		–	–	–
Assessment of understanding	✓	–		–	–	–
Protocol consent (eConsent)	✓	–		–	–	–
Medical history questionnaire ²	✓	✓		–	–	–
SARS-CoV-2 infection risk assessment ²	✓			Weekly		–
COVID-19 symptom surveillance ²	–			Weekly		–
Confirm eligibility	✓	–		–	–	–
Obtain demographics ²	✓	–		–	–	–
Randomize, Standard of Care Group only	–	✓		–	–	–
SARS-CoV-2 testing questionnaire ²	–			approximately 2x per week		–
End of study questionnaire ²	–	–		–	✓ ⁷	✓
Research Samples						
Serum for SARS-CoV-2 clinical serology ³	–	✓		✓	✓	–
Nasal swab	–			Daily ⁴		–
Vaccination procedures⁶						
COVID-19 symptom check ⁵	–	–		–	✓	✓
Vaccination	–	–		–	✓	✓

Greyed out visit does not apply to this group.

1 Screening may occur over the course of several contacts/visits up to and including day 1, prior to randomization.

2 Results from screening at school, if applicable, or at other locations will be captured via eDiary, please see Section 9.16.

3 From screening to the final study visit, the total blood volume to be collected from each participant will be approximately 15 mL (maximum) with a maximum of approximately 5 mL collected in a single visit. For blood self-collected by a participant the maximum volume will be less than 1 mL in a single collection. If a Main cohort participant is also in the Prospective Close Contact (PCC) cohort related to an index case or in the Case-ascertained Close Contact (CACC) cohort, one additional blood collection (self-collection) will be performed (see table below).

4 Daily swabs will be collected from D1 through D113. Swabs will be returned via drop-off location(s) specified by the clinic or through the mail.

5 COVID-19 Symptom Check to be performed within 24 hours prior to vaccination.

6 Vaccination procedures only apply to participants who have not received COVID-19 vaccine outside the study and for participants in the Vaccine Declined Group who request to be vaccinated.

7 Only applies to participants who are not receiving vaccination on study, ie, who have already received COVID-19 vaccine outside the study or who have declined vaccination (Visit 5 will be the last study visit for these participants).

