Baseline SARS-CoV-2 negative set (Main study primary data set): To account for ramping vaccine efficacy (VE), the protocol stipulated that primary analyses would be conducted among all baseline SARS-CoV-2 negative participants, and again among participants in the “Day 29 Negative Set”—the set of participants without seroconversion or PCR-confirmed infection on or prior to second vaccination on Day 29. The intent of this plan was to evaluate effects of the full two-dose vaccine regimen. Given that time of second vaccination is not easily defined in the SoC and Vaccine Declined groups and given that some participants in the Immediate Vaccination group began swabbing and accruing person-time and infection events before first vaccination, primary analyses will instead be conducted among all eligible enrolled baseline SARS-CoV-2 negative participants (Baseline SARS-CoV-2 negative set). All person-time and events will be included, and ramping VE will be accommodated using analyses that estimate vaccine effects according to number of doses received. Baseline SARS-CoV-2 negativity will be defined as PCR negative based on the first resulted (see section 3.2.9 for exclusions) nasal swab and seronegative based on the first qualifying (see section 3.2.8 for exclusions) blood sample closest to the first resulted swab. Note that blood collection for determining baseline serostatus was intended to occur coincident with initiation of swabbing; however, some participants had blood collected well before they began swabbing, and others had blood collected well after the initiation of swabbing. The analysis will summarize the distribution of time between first resulted swab and first blood. Qualifying blood sample closest to the first resulted swab date will be defined as either the closest qualifying blood sample on or before the first resulted swab date (if it exists) or the closest qualifying blood sample after the first resulted swab date (if no qualifying blood sample exists on or before the first resulted swab date). Primary analyses of vaccine efficacy against infection (VES) and of the vaccine effect on viral load (ΔVL) will be conducted among Baseline SARS-CoV-2 negative set participants that were enrolled as randomized.

All primary and secondary analyses will be done according to enrollment group, ie, Immediate Vaccination Group, Standard of Care Group, or Vaccine Declined Group.

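### SAP 9.2 ignores the protocol's post-dose pause in weekly symptom collection, which applies to the Immediate arm only, so COVID-19 disease is ascertained differently by arm

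*SAP*

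**What the plan says.** **Collection.** Protocol 9.15 limits the pause to one arm and gives the reason: "For Immediate Vaccination Group only: due to the overlap of symptoms that can result from vaccination and symptoms of COVID-19". The rule is: "monitoring will begin 7 days following the first study product administration. Symptom monitoring will be paused 7 days following the second product administration". Read alone, the second sentence could mean a pause that starts on day 7. The schedule in Appendix E settles it: "Weekly starts at week 2, not during week 5". The row "COVID-19 symptom surveillance" in Appendix F is weekly for Standard of Care (SoC) and Vaccine Declined, with no break.

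**Analysis.** SAP 9.2 says: "Rate tables and VE estimation analogous to analyses of the acquisition endpoint will be produced". In the acquisition analysis, SAP 3.1 states: "All person-time and events will be included". SAP 7.1 starts the one-dose and two-dose periods on the day after each dose.

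**Endpoint.** SAP 9.2 needs a positive PCR plus any one listed symptom between 3 days before and 14 days after the first positive swab. The list includes fever, chills, fatigue, aches and headache. The SAP departs from the protocol "to expand to also include daily symptom questionnaires that start after a positive test to increase precision of the disease definition". A symptomatic weekly log is taken to cover the whole time back to the preceding log, or to enrollment if there is none. A positive PCR with no symptoms, or with logs missing, is censored. The post-dose pause is not mentioned.

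**The concern.** The protocol recognised that symptoms in the week after a dose cannot be read as COVID-19 and stopped collecting them. The SAP then analyses the endpoint as if surveillance were continuous and equal in all groups. Two errors follow, and both can occur only in the Immediate arm.

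- **Missed cases.** A participant whose illness falls in a paused week and reaches no other log leaves the analysis as a non-case, while the paused days remain in the denominator. This raises VE_D.
- **Reactions counted as disease.** A PCR-positive participant without COVID-19 symptoms who has a vaccine reaction can qualify through a daily log or through the look-back. The one-symptom threshold makes this easier than the protocol's rule of two systemic symptoms or one from a more specific list. This lowers VE_D.

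The look-back can also give an onset date in the reaction week or in the wrong dose period. None of this is handled by the baseline covariates or the censoring weights of SAP 7.2, which address exposure and censoring, not symptom measurement.

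**Working it through.** The documents give no numerical figure for VE_D, so there is none to reproduce. The design count of 225 events concerns infection and does not enter.

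**1. Paused share of follow-up.** Inputs: doses at D1 and D29, swabbing to D113 (Appendix E), and the mutually exclusive periods of SAP 7.1.
- One dose: 29 − 1 = 28 days; 7/28 = 25%.
- Two doses: 113 − 29 = 84 days; 7/84 = 8.3%.
- Overall: 14/112 = 12.5%. SoC and Vaccine Declined: 0%.

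**2. Can a pause hide a whole case?** The symptom window is 3 + 1 + 14 = 18 days. A first positive swab on post-dose day 1 to 7 has a window that ends on post-dose day 15 to 21. So 8 to 14 days of resumed weekly surveillance always lie inside it. A case is lost only if its symptoms began and ended within the pause and neither a daily log nor the look-back picked them up.

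**3. How many infections are open to a reaction symptom?** The window reaches back into the 7 days after the latest dose for first positives on post-dose days 1 to 10 (10 − 3 = 7). That is 10/28 = 36% of one-dose days and 10/84 = 12% of two-dose days. A first positive in the 14 days up to dose 2 can also reach forward into the second reaction week, if the dose is still given.

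**4. Misdating by the look-back.** Assume, for illustration, weekly logs on days 28, 35 and 42, with the day 35 log paused in the Immediate arm. Dose 2 is on day 29, the first positive swab on day 31 (window days 28 to 45), and true onset on day 37.
- Without a pause: the day 35 log is clear, so the day 42 log is attributed from day 36. Onset is dated day 36.
- Immediate arm: the day 42 log is attributed back to the day 28 log. Onset is dated no later than day 29, which SAP 7.1 places in the one-dose period although the infection came after dose 2.

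A daily log starting on day 37 does not repair this, because SAP 9.2 takes the earliest symptomatic day from either log.

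**5. Illustrative limits.** Assumptions: constant hazard, the SAP 7.1 periods, and true VE_D of 50% (one dose) and 70% (two doses). The asymptomatic share *a* is 40% (Protocol 2.6).
- Missed cases, *d* = fraction of paused-week cases lost, *f* = paused share: apparent VE = 1 − (1 − VE)(1 − *f·d*).
- Reactions, *r* = fraction of asymptomatic infections with overlapping windows called disease, *s* = share from step 3: apparent VE = 1 − (1 − VE)(1 + [*a*/(1 − *a*)]·*s·r*).

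| Mechanism alone | One dose, true 50% | Two doses, true 70% |
|---|---|---|
| Missed, *d* = 25% to 100% | 53.1% to 62.5% | 70.6% to 72.5% |
| Reactions, *r* = 25% to 100% | 47.0% to 38.1% | 69.4% to 67.6% |

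For example, 1 − 0.5 × (1 − 0.25) = 62.5%, and 1 − 0.5 × (1 + 0.667 × 0.357) = 38.1%. By step 2, *d* = 100% is an extreme that the documents do not make plausible. They give no value for *d* or *r*.

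**The case against.** The strongest reply concerns size. A reader might infer that a quarter of one-dose cases are missed, so that a true VE_D of 0% would read as 25%, and as 8% for two doses. The documents do not support that. It equates paused days with lost events, whereas the symptom window always runs well past the pause, daily logs run for 14 days or until symptoms resolve (Protocol 9.7), and the look-back treats the first resumed log as covering the pause. The recall period of the weekly log is not given, so the actual loss cannot be computed. This part of the reply stands in full.

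The reaction route is also limited. Every counted case is PCR-positive, so a fever soon after a dose may be genuine COVID-19. Daily logs start only on notification of infection. A symptom check within 24 hours before each dose, and the protocol's reliance on CDC guidance for diagnosed participants, reduce dosing of people already infected. These points narrow the route but do not close it.

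The two-dose figures rest on the exclusive periods of SAP 7.1. In the Cox model of SAP 7.2 as printed, both dose indicators are on after dose 2, so 1 − exp(α₂) compares two doses with one. If every paused-week case were lost, exp(α₂) would be multiplied by (77/84)/(21/28) = 1.22, which pushes that quantity down. The two-dose column above does not describe it.

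Finally, VE_D is secondary, the SAP calls the study underpowered for its primary objectives, and SAP 9.2 admits that some participants' diaries were incomplete or not collected in the interval. That disclosure does not say that one arm's gap was planned, and low power widens an interval without removing a systematic difference between arms.

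**Conclusion.** The point holds as a difference in ascertainment. Followed as written, SAP 9.2 measures disease under one surveillance scheme in the Immediate arm and another in SoC, and it ignores the protocol's own reason for the difference. The firm numbers are the shares of follow-up: 25% of one-dose time, 8.3% of two-dose time under the exclusive periods, and 0% elsewhere. The bias itself cannot be sized from the documents and is smaller than those shares suggest. A reader might also infer that VE_D is inflated. That is not supported, because the two mechanisms pull in opposite directions and nothing in the documents shows which dominates. The effect is of practical interest mainly for the one-dose estimate; for two doses even the extremes move a true 70% by no more than about 2.5 points. The change should be made before VE_D is reported, but it does not touch the primary infection endpoint.

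**What to change.** In SAP 9.2:

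- Make the 7 days after each actual study-dose date a gap in start-stop follow-up for the disease endpoint, with its events and person-time removed. Anchor the gap to dose dates rather than study weeks, since dose 1 can follow enrollment by days and dose 2 has a window of −3 to +14 days (Appendix I).
- Accept no onset day inside a gap from any log, and do not carry the weekly look-back across a gap.
- State one rule for infections first PCR-positive in or just before a gap. One option is to censor at the start of the gap, with a sensitivity run that counts symptoms persisting or starting after it.
- Report VE_D with and without the gap, and disclose that surveillance differed by arm by design.
- Optionally, apply comparable gaps in SoC as a supportive run, described as approximate. Fixed study days there would not reproduce the Immediate arm's surveillance, because dose dates vary and the Cox model runs on calendar time.

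The cost is SAP wording and one change to the start-stop data set. Up to two weeks of Immediate-arm person-time per participant, and any true cases in them, leave the analysis. Because the SAP was drafted after unblinding (SAP 2.4), the rule should be written down and dated rather than settled during programming.
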